Research Nurses will identify appropriate patients using a screening tool that will outline the inclusion/exclusion criteria. Participant Information Sheets (PIS) will be provided to patients and their families for their appropriate ages. They will be offered a copy of the results if they would like and will be told how the results will be reported when the study is completed.

After gaining written consent from the parent and written or verbal assent from the child, Wong-Baker pain scoring methods will be explained in advance of the procedure. Necessary data will be collected for the CRF.

The participant's involvement in the study will be limited to the length of time of their Emergency Department visit, so will be just one day and one procedure.

For the experimental (music) group, Cascade's musicians will spend eight weeks, twelve hours per week in the ED and will aim to recruit all eligible children during that period. As this is a pilot study recruitment targets need to remain flexible, but are estimated at 60-80 participants (per group).

The same number of participants will be recruited to the control (no live music) group as a comparison, on days that the musicians are not in the department. All patients in both groups will continue to receive standard care. Each child can only be in the study once and for one procedure. Patients will be free to withdraw from the study at any time.

Following the procedure and interviews, patients involved will be offered a sticker and a CD of calming music recorded by Cascade Music as a thank you for their participation. For ethical reasons, this will not be mentioned in advance.

Timeline:

December 2018:

Implementation of study including finalising ethical approval

Recruitment of Research Nurse,

Publicise study within Alder Hey Children's Hospital's Emergency Department.

January - March 2019:

Recruitment of participants to the study, both experimental (music) and control (non-music) groups.

Data collection from participants.

March - May 2019:

Complete data analysis

Write report

Explore dissemination options including publishing and conferences

Plan next funding application

Methods of data collection and analysis

Three sets of data will be collected:

1. Quantitative: Self-reported pain.

A validated observational tool will be used: Wong Baker Faces.

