This is suitable for children age 3+. As children self-report, the Research Nurse will collect this data on a paper CRF. Wong Baker scores will be collected before, during and after the procedure. If mid-procedure collection of pain score is inappropriate, then participants can be asked about mid-procedure pain scores after the procedure.

A self-reported pain score will also be taken in advance, during the recruitment process, to provide a baseline measure.

2. Quantitative: Observed pain.

Data will be collected on observed pain levels using a validated observational tool: Faces, Legs, Activity, Cry and Consolability (FLACC) pain assessment tool.

This tool is suitable and validated for all ages of the recruited participants, from 6 months until 16 years. References regarding justification of this scale for these age ranges are below.^{5 6}

Scoring will take place before, during and after the procedure.

The Research Nurse will carry out this scoring, and when available, an independent observer from the Emergency Department staff will also. The Research Nurse will collect this data on the paper CRF.

Heart rate will also be monitored throughout, where a child is cooperative enough. HR will be noted approximately every two minutes before, during and after procedure, (cleaning marks the beginning of the procedure, final bandage/dressing marks the completion). The Research Nurse will note HR data on the CRF. There will be an option for the Research Nurse to record 'not available' for heart rate measurements either because child refuses or because of probe or monitor issues etc.

3. Qualitative: Distress and experiences of patients, families and clinicians.

Our outcome measures will include collecting qualitative information on patient's distress, and patients', families' and clinician's Emergency Department experience. All recruited patients will receive a paper questionnaire with open text response options.

Qualitative questions for Experimental AND Control Groups:

The following two questions will be asked of both the experimental (live music) AND control (no live music) groups. The questions will be asked of each of these two people: patient and parent/legal guardian.

'Please answer the following questions, in particular, in regard to distress levels/lack of distress':

- Qualitative question 1. What do you think helped you/your child during their procedure?

- Qualitative question 2. Did anything make the situation worse?

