Record the duration of the procedure (cleaning marks the beginning of the procedure, final bandage/dressing marks the completion)

Record how many attempts were required to carry out procedure

Record the role and grade of the Clinician carrying out the procedure

Record heart rate at 2-minute intervals if tolerated. Include option for the research nurse to record 'not available' for heart rate measurements either because child refuses or if probe or monitor issues etc

Is there an independent observer present? If so, who?

Inclusion criteria

Parent/Legal Guardian present and able to consent.

Age range: 6 months - 16 years. (see references at end notes 5&6 below)

Procedures: Capillary blood sampling, cannulation, venepuncture, suturing, wound cleaning and closure.

Families and children whose primary language is other than English will be included in the study if their English speaking skills are at a level that they can understand and complete the consent/assent process.

Exclusion criteria

Children with Special Educational Needs, children with global development delay, sensory impairments, neurological deficits or disorders, impairment to pain i.e. spina bifida.

Children in resuscitation or unconscious.

Non-English speaking.

Suspected ingestion of recreational drugs, antidepressants or alcohol

Concerns relating to NAI (non accidental injury)/safeguarding concerns

Life or limb critical injuries

Children too unwell to participate

Recruitment

Research Nurses will identify appropriate patients using a screening tool that will outline the inclusion/exclusion criteria. For inclusion in either group, a parent or legal guardian must be available to give consent, collected by the Research Nurse.

The Research Nurse will introduce the study to potential recruits, and supply and explain Participant Information Sheets. Posters will be displayed within Alder Hey's Emergency Department to promote the study and give some initial details.

The same number of participants will be recruited to the control (no live music) group as a comparison, on days that the musicians are not in the department. All patients in both groups will continue to receive standard care. Each child can only be in the study once and for one procedure. Patients will be free to withdraw from the study at any time.

Ethics and governance

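### The 'during' FLACC score is not tied to any event, so a scorer who can see the group chooses the moment; heart rate on a two-minute clock is a lesser form of the same gap

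*Protocol*

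**What the plan says.** Under Methods of data collection and analysis, item 2 (Observed pain), the timing of FLACC is given in one sentence: "Scoring will take place before, during and after the procedure". On who scores, the same item says "The Research Nurse will carry out this scoring, and when available, an independent observer from the Emergency Department staff will also".

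Heart rate has its own rule there: "HR will be noted approximately every two minutes before, during and after procedure". The limits of the procedure follow in brackets: "cleaning marks the beginning of the procedure, final bandage/dressing marks the completion". The CRF list under Target population and sampling repeats the interval ("Record heart rate at 2-minute intervals if tolerated"), uses the same limits for the recorded duration, and adds "Record how many attempts were required to carry out procedure".

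The inclusion criteria cover a wide range: "Procedures: Capillary blood sampling, cannulation, venepuncture, suturing, wound cleaning and closure". Control children are recruited "on days that the musicians are not in the department" (Methods; repeated under Recruitment).

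The protocol does not link the 'during' FLACC or any heart rate reading to skin puncture, first stitch or another event. It does not ask for a worst score, a fixed window, or a score per attempt.

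**The concern.** The research question is whether live music lowers pain and distress in children undergoing a procedure, and the 'during' score answers it most directly. Two nurses could both follow the protocol exactly while one scores at skin preparation and the other at needle entry.

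Two things are at stake. If the moment varies without regard to group, the comparison becomes noisier. If it varies with group, the difference between groups partly reflects when children were scored. The second is possible because the scorer can see the group.

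Wong-Baker does not fill the gap. It is used from age 3, and its mid-procedure score may be asked for afterwards. For children from 6 months to under 3 years, FLACC and heart rate are the only quantitative pain measures.

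The moment of measurement is a rule for collecting data. If neither the moment nor its timing is captured at the bedside, an analysis plan cannot restore it.

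**Working it through.** The protocol gives no procedure durations, FLACC mean, SD, effect size or power, so there is no figure of its own to reproduce. The check has three parts.

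**1. What the text allows for FLACC**
- The scoring sentence names three phases and nothing finer.
- The only limits given for a procedure are cleaning and final dressing. They are attached to heart rate and to recorded duration, not to the FLACC sentence. Applying them to FLACC is a reasonable reading, but an inference.
- The scorer is the Research Nurse, with a second observer from department staff when one is available. Neither is given a timing rule.
- The protocol does not use the word unblinded. Visibility of the group follows from live music against no music, with controls taken on other days. No masked or video scoring is described. The second observer is in the same position.

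The share of children scored away from the painful step cannot be computed. It could be 0% if nurses always score at the needle, or 100% if they always score at cleaning.

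**2. What discretionary timing could do (illustration)**

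Assumed: mean FLACC is 6 at the painful step and 2 elsewhere, and music has no effect. If a fraction p of a group is scored at the step, the group mean is 2 + 4p.

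- Bias = 4 × (p in controls − p in music). With p = 0.50 in the music group:
  - controls 0.60: 4 × 0.10 = 0.4 points
  - controls 0.70: 4 × 0.20 = 0.8 points
  - controls 0.80: 4 × 0.30 = 1.2 points
- If the step were caught more often in the music group, the sign would reverse.
- If p is the same in both groups there is no such bias, but timing alone adds an SD of 4 × √(p(1 − p)): 2.0 points at p = 0.50 and 1.6 at p = 0.80.

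These show the mechanism and its scale under the assumptions. They do not estimate what will happen.

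**3. Heart rate on a two-minute clock**

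Input from the protocol: an interval of 120 seconds. Assumed: the clock runs independently of the painful moment (random phase).

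- Reading within 15 s either side of a brief puncture: 30/120 = 25%.
- Reading within 30 s either side: 60/120 = 50%.
- At least one reading inside a painful step of w seconds: min(1, w/120).

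| Painful step (s) | Children with a reading inside it |
|---|---|
| 10 | 8% |
| 30 | 25% |
| 60 | 50% |
| 90 | 75% |
| 120 or more | 100% |

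The interval is only approximate. With each reading shifted at random by up to 30 s either way, simulated coverage is 74% at 90 s, 92% at 120 s and 100% at 180 s. The gap therefore concerns brief needle steps and closes for painful parts lasting two minutes or more, or slightly longer with an irregular clock.

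**The case against.** **Nurses may already score at the needle.** They may well do so without being told, and the CRF may prompt them. The protocol says FLACC goes on the paper CRF, yet its CRF list has no FLACC entry, so that list is not the whole form. This stands. A reader might infer that many children are measured away from the painful step, or that the moment is never fixed or recorded. Without durations or the form, neither can be shown. What can be said is that the protocol text does not require any particular moment.

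**Heart rate was not meant to capture the puncture.** It is to be followed over the whole procedure, and nothing names the puncture as its target. This also stands, and it makes heart rate the secondary point. A reader might infer that readings usually miss the puncture, but that depends on the tolerance chosen: 25% are close at 15 s and 50% at 30 s. Nor does it follow that short procedures have no reading at all. That needs a whole procedure, cleaning to dressing, of under two minutes and a clock unrelated to its start. If the clock starts at cleaning, every procedure has one.

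**This is a pilot.** Its aims are exploratory, recruitment is flexible and no power is claimed. Turning timing noise into lost power would need an SD, an effect and a noise level that the protocol does not give, so no power figure is offered.

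**A highest-score rule can mislead.** A maximum over the whole painful step tends to rise with its length, so it would mix intensity with duration and leave open which attempt counts. This is right, and the fix answers it with a fixed window on the first attempt.

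**A second observer is planned.** That helps with agreement between scorers when one is present, but not with the choice of moment or with masking.

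**Conclusion.** The point holds as a cheap improvement to the measurement rule, of minor severity. The protocol leaves the moment of the 'during' FLACC to a scorer who can see the group, over a span that can reasonably be read as cleaning to final dressing and across very different procedures. This can add noise and, if timing differs by group, bias.

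Its size in this trial is unknown. The illustration of 0.4 to 1.2 points rests wholly on assumed means and assumed differences in timing. The heart rate figures rest on the stated two-minute interval and an assumed random phase, and they matter only for brief painful steps. The documents do not show that bias will occur, or in which direction.

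**What to change.** In Methods of data collection and analysis, item 2:

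- Define the 'during' FLACC as the highest score in one short window of fixed length, for example the first 30 seconds, starting at a named event on the first attempt: first skin puncture, first stitch or first wound contact, according to the procedure.
- State that the rule is the same in both groups and for both observers.
- Keep the two-minute heart rate series, and add one reading at that same event where obtainable, with a CRF line for it.

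The cost is a sentence or two in the protocol and one CRF line, with no extra staff. The downside is that the nurse must watch for one defined event, at a time when a mid-procedure Wong-Baker score may also be due. The rule removes the choice of moment but does not blind the scorer, so reports should still describe the FLACC comparison as unblinded.

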Music may have a positive impact on pain and distress for children undergoing intravenous placement. Benefits were also observed for the parents and health care providers.

This study uses similar methods and looked for similar outcomes as Music:Ed, but using recorded rather than live music, and in a non-emergency setting.

The Music:ED study will therefore use a controlled experimental design to investigate the impact of using therapeutic live music in the Alder Hey Paediatric Emergency Department to reduce pain and distress during interventional procedures.

The outcomes of the study will provide evidence for the use of live music in the PED to support and enhance patient experience. Distress is often particularly high within the emergency department. If a patient's experience whilst attending the Emergency Department can be less traumatic, this will be of benefit to all: patients, families and clinicians. A patient who is less distressed is more cooperative and may be easier and quicker to treat.

Methodology and Methods

Research Question

Does live music decrease the pain and distress of patients undergoing a procedure within the paediatric emergency department?

Aims of the Study

Our aims/objectives include:

1. To explore whether live music helps to decrease pain and distress in patients in the Paediatric Emergency Department
2. To explore whether procedures can be carried out with greater ease from a clinician's perspective and whether staff experience of the situation is impacted by the presence of live music.
3. Exploring the overall impact on the ED experience from the patients, families and clinicians' perspectives.

Methodological Approach

We have chosen a mixed method design to provide us with different forms of data and insights from multiple practitioner, parent and patient perspectives throughout the experience.

Quantitative data includes collecting information about the patient's pain levels and qualitative data will be collected from open response questionnaires to explore patient distress and the practitioner, parent and patient perspectives on the experience.

Methods

There will be an experimental (live music) and a control (no live music) group.

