Qualitative questions for Experimental Group Only:

Within the experimental group only, the following three additional questions will be asked, via a paper questionnaire, of each of these three people: patient, parent/legal guardian and clinician. These questions directly link to the objectives of the study.

These questions are in particular regard to music, which is why they would not be appropriate to be asked of the control (no live music) group.

- Qualitative Question 1. How did you feel the music affected the child's distress before, during and after the procedure?

- Qualitative Question 2. Can you tell me about how the live music helped or hindered the procedure?

- Qualitative Question 3. Can you tell me about your experience of the ED (Emergency Department) today, in particular in regard to the music?

The qualitative questions will be included in a open ended questionnaire style sheet which the parent, child or practitioner if the parent wishes, can fill out between the end of the music intervention and when they are discharged from the ward. It will be collected by the RN and stored in a secure room in a locked filing cabinet.

Target population and sampling

This will be a single centre study.

Study participants for both the control and experimental groups of the study will be recruited from AHCH Emergency Department. The study population will consist of children between the age of 6 months and 16 years needing to undergo a painful procedure from a specified list. The Research Nurse will use a screening tool to assess eligibility within this age group.

Necessary data will be collected for the CRF by the Research Nurse:

CRF:

Patient's name

Patient's age

Patient's gender

Parent(s)/legal guardian in attendance during procedure (names)

Whether or not the patient has had this procedure before

How many times the child has visited the hospital in the last 12 months

Have they had an upsetting hospital experience in the past? Yes or no

Record a Wong-Baker pain score at this point (for children age 3+) as a baseline measure

Record whether patient has had analgesia in advance, or during hospital visit

Record use of local anaesthetics e.g EMLA/amecop, LAT gel, cold spray (ethyl chloride)

Record use of Entonox during the procedure

Record if other distraction methods were also used

(Play Specialist/books/bubbles/IPad/TV/ iPhone/ staff dancing and singing, etc)

Record whether the procedure was successful

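### Music questions 1 and 2 presuppose that the live music had an effect, whereas the study's aims ask whether it had one

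*Protocol*

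**What the plan says.** Under Qualitative questions for Experimental Group Only, the protocol sets out three questions to be asked "of each of these three people: patient, parent/legal guardian and clinician". They are:

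- Music question 1: "How did you feel the music affected the child's distress before, during and after the procedure" (the words at issue are "How did you feel the music affected")
- Music question 2: "Can you tell me about how the live music helped or hindered the procedure"
- Music question 3: "Can you tell me about your experience of the ED (Emergency Department) today, in particular in regard to the music"

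The protocol gives these questions weight: "These questions directly link to the objectives of the study". The format is open text: "All recruited patients will receive a paper questionnaire with open text response options".

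Two further questions, on what helped and on whether anything made things worse, go to patients and parents or guardians in both groups. Respondents are told to answer them with distress in mind, and neither names music. Clinicians are not listed as respondents to these two.

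The research question, and Aims 1 and 2 under Aims of the Study, are phrased as whether: whether music lowers pain and distress, and whether procedures go more easily from the clinician's point of view. Under Methodological Approach, distress is assigned to the questionnaires: "qualitative data will be collected from open response questionnaires to explore patient distress".

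**The concern.** A study that asks whether something happened should not collect its evidence with a question that assumes it did. Someone who noticed no change has to reject the premise of music question 1 in order to say so. Some will do that readily. Others, including children, may instead look for an effect to describe.

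The wording carries weight here for two reasons. First, the protocol presents its scales, Wong-Baker and FLACC, as pain measures and leaves distress to the questionnaires. Second, the music questions go to the music group alone, so no control answers to the same questions exist that could show how much of what is reported comes from the wording. Thematic coding cannot separate the two afterwards.

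**Working it through.** No arithmetic applies to the main point, and the protocol gives no figure to reproduce. The check is to read each of the five fixed questions against the same tests.

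| Question | Asked of | Names music | Presupposes that music had an effect | Asks about distress | Invites a no-change answer |
|---|---|---|---|---|---|
| Shared 1 (what helped) | patient and parent, both groups | no | no (assumes something helped, but not the music) | yes, by the instruction | no |
| Shared 2 (anything worse) | patient and parent, both groups | no | no | yes, by the instruction | yes, it can be answered no |
| Music 1 | patient, parent, clinician; music group | yes | yes, direction left open | yes | no |
| Music 2 | patient, parent, clinician; music group | yes | yes, both directions named | no, asks about the procedure | no |
| Music 3 | patient, parent, clinician; music group | yes | no, only steers attention to the music | no | neither invites nor discourages it |

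Four things follow.

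1. Two of the three music questions presuppose an effect. Music question 3 does not.
2. Music question 1 is the only question that links music to distress directly, and it is one of the two.
3. Neither question 1 nor question 2 presupposes a benefit. Question 1 leaves the direction open, and question 2 names hindrance alongside help.
4. The respondents differ in what else they are asked. Patients and parents also get the two shared questions, where a family that saw no effect can simply leave music out. Clinicians get only the music questions. Aim 2 concerns ease of the procedure as the clinician sees it, and music question 2 is the only one that asks about this directly. The case report form records duration, number of attempts and success, but not the clinician's opinion.

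On reach, the recruitment estimate is 60-80 children per group. Three respondents for each music-group child would give 60 × 3 = 180 to 80 × 3 = 240 sets of answers. That is a ceiling. Eligibility starts at 6 months, so some patients cannot answer, and the description of the sheet can be read as leaving it to the parent, the child or, if the parent wishes, the practitioner to complete.

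**The case against.** The strongest reply is that this is an exploratory pilot with open-text questions. There are no tick-boxes from which an option could be missing, and anyone can write that the music made no difference. The shared questions already give patients and parents a less leading route on distress, with a control group to compare against. No quantitative outcome is touched.

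Much of this stands, and it rules out several stronger readings that a reader might infer:

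- *Respondents cannot report no difference.* They can. The fault is a leading premise, not a missing response category.
- *All the music questions are leading.* Question 3 assumes no effect.
- *Reported benefit is inflated.* The wording tilts towards some effect. A tilt towards benefit would need a further assumption, such as courtesy towards the musicians or towards the nurse who collects the sheet. That is plausible, but the protocol does not establish it, and it could operate under any wording.
- *These are the only data on distress.* The shared questions are also framed on distress, in both groups.
- *The themes will be presented as proof that music works.* The protocol says no such thing. It plans an interpretive thematic analysis and plans no rate of reported benefit.

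What the reply does not answer is the mismatch between the aims and these two questions, or the position of clinicians, for whom there is no less leading question to fall back on.

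**Conclusion.** The point holds in a limited form. Music questions 1 and 2 presuppose an effect that the aims set out to examine, and the protocol itself fixes their wording, so this is not a matter left to an analysis plan. The lean is towards reporting some effect, and its size cannot be derived from the protocol. It matters most for the clinicians' answers on Aim 2 and least for parents and patients, who have the shared questions as well.

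The conclusion rests on one assumption: that at least some respondents follow the premise of a question rather than reject it. If the wording stays as it is, answers to question 1 should not be read on their own as evidence that an effect exists. This is a minor and inexpensive improvement, worth making before data collection because the analysis cannot undo the wording afterwards.

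**What to change.** Reword two questions in the protocol and on the questionnaire sheet:

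- Music question 1: ask whether the music made the child's distress less, more or no different before, during and after the procedure, and why.
- Music question 2: ask whether the live music helped, hindered or made no difference to the procedure, and how.

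Leave music question 3 and the two shared questions unchanged, and keep the open-text format. No separate hand-in step for the shared questions is needed on this account: the protocol fixes no order for the questions, and no ordering fault has been shown.

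The cost is slightly longer questions, a reprint of the sheet and notification of the ethics committee.

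### The CRF list does not specify recording which eligible procedure was done, although the groups are formed by day and the procedures differ widely

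*Protocol*

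**What the plan says.** The CRF list stands in the Protocol under Target population and sampling. Four of its items refer to a procedure without naming it:

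- "Whether or not the patient has had this procedure before"
- "Record whether the procedure was successful"
- "Record the duration of the procedure"
- "Record how many attempts were required to carry out procedure"

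The list also covers the clinician's role and grade, analgesia, local anaesthetic, Entonox and other distraction. It has no item for the procedure performed and none for the date.

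Under Inclusion criteria, the eligible procedures are "Capillary blood sampling, cannulation, venepuncture, suturing, wound cleaning and closure". Under Methods and again under Recruitment, controls are enrolled "on days that the musicians are not in the department". The recruitment estimate is 60 to 80 per group, described as flexible because this is a pilot.

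Data Analysis names the chi-square test for trend, paired t-tests and Wilcoxon signed-rank tests. It mentions no matching, stratification or covariate adjustment.

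**The concern.** Pain during a procedure is a main outcome, and it is reasonable to expect it to depend on what the procedure is. That is a judgement, not a statement in the protocol. The groups are defined by whether the musicians are in the department that day, and nothing in the design balances procedure mix between the two kinds of day: there is no randomisation, matching or quota. If the mix differs systematically, part of any difference in pain scores reflects the procedures and not the music. The bias can go either way, so it could create an apparent benefit or hide a real one.

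The other CRF items do not replace procedure type. The baseline Wong-Baker score is taken at recruitment, and only from age 3. Duration, attempts and success are observed after the group is fixed. The second aim asks whether procedures become easier with music, so adjusting for these items could remove part of a real effect.

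An SAP can prescribe adjustment, but it cannot supply a variable that was not collected. The gap therefore belongs to the protocol.

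**Working it through.** **Text check.** I read each item of the CRF list, and each other statement about data capture, for procedure type.

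- CRF list: procedure type is absent.
- Methods of data collection and analysis: this section puts FLACC scores and the repeated Wong-Baker scores on the paper CRF, and it does not mention procedure type.
- Methods, and Recruitment: a screening tool covers the eligibility criteria, which include the procedure list. Neither section says that its content is kept as study data.
- Data Protection: the Research Nurse, PI and treating clinician may see the child's records. No extraction of procedure type is planned.

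**Size.** The protocol gives no SD, effect size, alpha or power, so there is no figure of its own to reproduce. What follows is an illustration. Only the 60-80 per group comes from the document. Assumed: 0-10 scoring, SD 3, a pain gap of 2 or 3 points between procedure types, a systematic difference of 20 percentage points in the share having the more painful type, no music effect, and a two-sided 5% two-sample normal test.

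Spurious difference = gap × difference in share:

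- 2 × 0.20 = 0.4 points
- 3 × 0.20 = 0.6 points

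Standard error = SD × √(2/n):

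- n = 60: 3 × √(2/60) = 0.548
- n = 80: 3 × √(2/80) = 0.474

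Rejection rate = 1 − Φ(1.96 − bias/SE) + Φ(−1.96 − bias/SE):

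| Bias | n = 60 per group | n = 80 per group |
|---|---|---|
| 0.4 | 11.3% | 13.5% |
| 0.6 | 19.5% | 24.4% |

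**Sensitivity to the assumptions.**

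- SD 3, 10-point difference in share, gap of 1 point (bias 0.1): 5.4% and 5.5%.
- SD 3, 10-point difference, gap of 2 points (bias 0.2): 6.5% and 7.1%.
- SD 2.5, 20-point difference, gap of 2 points (bias 0.4): 14.2% and 17.3%.
- SD 2.5, 20-point difference, gap of 3 points (bias 0.6): 26.0% and 32.9%.
- SD 2.5, 30-point difference, gap of 3 points (bias 0.9): 50.5% and 62.4%.

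The result runs from almost no inflation to a large one, depending on imbalance and gap.

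**The case against.** The strongest reply is that the list is not the whole CRF. FLACC scores and the later Wong-Baker scores go on the CRF but are not in the list, and the list has no item for study group either. Absence from it therefore does not prove that procedure type goes unrecorded. The procedure is also an inclusion criterion checked for each child, the CRF carries the child's name, and team members may see the records. Each child contributes one procedure at one visit, so a look-up is plausible.

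This stands against a stronger reading. A reader might infer that the data will not exist and that the confounding could never be repaired. The documents do not show that. They show that recording is unspecified, not that the variable is unavailable. The reply does not remove the gap, however. The pain scores missing from the list are assigned to the CRF elsewhere in the protocol, and procedure type is not. Recovery would rest on sources with no planned extraction, while the study data are to be anonymised.

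A reader might also infer that chance differences in procedure mix inflate the error rate. They do not: chance imbalance is part of the sampling variance and is already covered by the nominal 5%. Only a systematic difference between musician and non-musician days does harm, and nothing in the protocol shows that one exists.

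Three limits on the illustration also stand. The two-sample test is not one that Data Analysis names. Self-report starts at age 3 while enrolment starts at 6 months, so fewer than 60-80 per group are likely to contribute Wong-Baker scores, and the inflation there would be smaller. Finally, a fine stratification across all listed procedures would be thin at this sample size.

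**Conclusion.** The point holds as a gap in specification. Nowhere does the protocol provide for recording which eligible procedure was performed, while its groups are formed by day and its procedures are mixed. A systematic difference in mix could then pass for an effect of music, and the means to check or correct it is not assured. Pilot status does not dispose of this, because the research question is whether live music decreases pain and distress.

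The size is conditional. The 0.4-0.6 point bias and the error rate of about 11-24% rest wholly on the assumed SD, pain gap and systematic imbalance. They show what could happen, not what is expected.

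**What to change.** - Add to the CRF list the procedure performed, using the categories under Inclusion criteria, and the date.
- In Data Analysis, state that procedure mix will be reported by group.
- Present the music-versus-control pain comparison adjusted for procedure type. Group it broadly, for example needle and blood-sampling procedures versus wound procedures, because the groups are small.

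The cost is one or two fields known at the bedside and slightly more analysis work, with no extra patients. The date lets the team check whether procedure mix follows a day pattern. The fields are best added before recruitment starts, since later recovery would depend on screening forms or records.
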